Our research group recently conducted a large-scale multicenter randomized controlled trial of electronic alerts for AKI throughout the Yale New Haven Health System from 2018 to 2020. The trial, which enrolled 6,030 patients with AKI, as defined by an increase in creatinine of 0.3mg/dL over 48 hours or 50% over 7 days, randomized patients between usual care and an intervention group whereby providers received a general AKI alert informing them to the presence of AKI and the patient's recent creatinine trends, and provided a link to an AKI-specific order set. Our study showed that, overall, alerting physicians to the presence of AKI did not demonstrate a difference in the rate of our primary outcome of progression of AKI, dialysis, or death, nor were there any differences in process measures accessed (i.e. provider actions) between the two groups, however, there was substantial heterogeneity among the study sites. Stratification of results by hospital revealed that signals of harm exist in the two non-teaching hospitals of our study, where a higher relative risk for our primary outcome was seen in the intervention group. This increased risk was shown to be driven by an increased number of deaths in the alert group, however, process measures still remained unchanged. The alert in this study was limited by the fact that it was purely informational. While an order set was provided, there were no associated patient-specific recommendations or guidance. Given the highly heterogeneous nature of AKI, a more personalized approach may be warranted. Further, this study enrolled all patients who developed AKI rather than a targeted subset of patients who may benefit, such as those AKI patients receiving potentially harmful kidney-toxic medications.

[figure not shown]
In the present proposal, we seek to expand upon our prior study to determine if the use of medication-targeted electronic alerts will modify provider behavior, particularly in regards to nephrotoxic medication use and cessation, in the care of hospitalized patients with AKI and/or reduce the rates of progression to AKI, dialysis, or mortality in hospitalized patients. Given the heterogeneous and surprising results of our prior study, it is of utmost importance that the efficacy of such interventions, even those that are seemingly benign, are rigorously evaluated in the setting of a randomized controlled trial.

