Other secondary study endpoints will look at a variety of patient outcomes as well as best practice metrics, including the following:

- Inpatient mortality
- Inpatient dialysis
- Discharged on dialysis
- Percent who progress to stage 2 AKI
- Percent who progress to stage 3 AKI
- AKI duration
- 30-day readmission rate
- Cost of index hospitalization
- “Best practice” outcomes: Proportion achieved per patient during index hospitalization:
 - Contrast administration
 - Fluid administration
 - Aminoglycoside administration
 - NSAID administration/cessation
 - ACEi administration/cessation
 - Urinalysis order
 - Documentation of AKI
 - Monitoring of creatinine
 - Monitoring of urine output
 - Renal consults

All investigators will be blinded to the treatment assignment until the end of the trial period.

Clinician Outreach:

While the unit of randomization is the patient, clinicians are considered subjects of this research. We will engage in pre-trial and periodic outreach to all clinicians who may be exposed to this study, informing them of the nature of the study, the fact that it is a randomized trial, and that alerts do not fire for all patients with AKI. We will additionally inform them that limited data is being collected regarding provider behavior. However, we will also make it clear that data subject to clinician behavior (continuation or discontinuation of any medication) will NOT be linked to individual clinicians. All such data will only be analyzed in aggregate. This outreach will be performed through short presentations at divisional conferences and meetings and through regular visits to hospital floors to engage directly with providers. A study Information Sheet will also be handed out to clinicians.

Study Timeline:

We plan to activate our medication-targeted alert in a step-wise fashion throughout our 4 study hospitals. Staggered enrollment will allow for proper pre-trial education as well as adequate site visits, study monitoring, quality control and clinician engagement at each site as roll out begins.

5. Genetic Testing N/A

A. Describe

- i. the types of future research to be conducted using the materials, specifying if immortalization of cell lines, whole exome or genome sequencing, genome wide association studies, or animal studies are planned *Write here*
- ii. the plan for the collection of material or the conditions under which material will be received *Write here*

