- Under-treatment: Patients randomized to medication-targeted alerts may have these medications discontinued more often. This should be beneficial, as the medications chosen have been associated with AKI. But it is also possible that, in some situations, discontinuation of medicine might engender risk (for example, discontinuation of a proton-pump inhibitor among patients with a gastrointestinal bleed). The internal DSMB has identified the following risks of discontinuation for each medication class with an associated monitoring plan to ensure that differential discontinuation does not cause harm to patients:

Nephrotoxin	Risk(s) of Discontinuation	Monitoring Plan
NSAID	
 -Increased use of opioid analgesics -Worse pain 	
 -Morphine-equivalent opioid exposure per patient-day -Use of naloxone and/or naltrexone -Intubation -Nursing-reported pain score
ACE/ARB/Renin	
 -Hypertension -Pulmonary Edema -Heart Failure 	
 -Blood pressure -Intubation -Chest X-Rays

PPI	
 -GI Bleed -Pain -Severe anemia 	
 -Echocardiogram -Blood Transfusion -Endoscopy Procedures -Nursing-reported pain score
-----	--	--

- Inattention to AKI: It is possible that, as providers learn that alerts exist, they become less attentive to the presence of AKI in patients randomized to the usual care group. We limit this risk by including the language "THIS ALERT DOES NOT FIRE FOR ALL PATIENTS WITH AKI" in each alert. Additionally, our educational efforts (which target each hospital division before the trial and biannually after initiation) make explicit the fact that these alerts are being conducted in a randomized framework.

-Alert Fatigue: These studies represent an additional alert to which providers will be exposed and prior research has demonstrated that more frequent alerting may lead to less attention to other alerts. While a potential risk, this is also a major motivation of this line of research, as only via randomized trials can truly effective alerts be discovered. Should no effect be found in these studies, AKI alerts will not be continued at the institutions.

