- To minimize the risk of undertreatment, the internal DSMB has identified outcomes of interest for each of the medication classes to ensure that differential discontinuation is not causing harm and will utilize their authority to suspend an arm of the study should harm be detected. Additionally, medication-targeted alerts will contain language that illustrates patient populations wherein continuation of the medication may be warranted (please refer to Data and Safety Monitoring Plan document).
- To limit the risk of inattention to AKI, we include the following language on the alert screen: "THIS ALERT DOES NOT FIRE FOR ALL PATIENTS WITH AKI". Additionally, our educational efforts (which target each hospital division before the trial and biannually after initiation) make explicit the fact that these alerts are being conducted in a randomized framework.
- Based on the new information obtained from our recent general AKI alert study which showed signals of harm in the non-teaching hospitals, we are taking necessary precautions to maximize patient safety in this trial. This proposed trial does involve a unique and more specific population than that of our prior study, and utilizes a different intervention which offers more individualized recommendations and guidance for clinicians.

As a preliminary assessment of safety of our drug-targeted alert, we analyzed a subset of data from our initial alert trial, including only patients who meet criteria for the current study (those AKI patients who had at least one dose of one of our targeted nephrotoxic medications within the 24 hours prior to AKI development). The results, both overall and stratified by hospital, are shown below:

Outcome Table

Variables	Control (N=1244)	Alert (N=1250)	p-value
Primary Outcome			.
AKI Progression, Dialysis or Death	205 (16.5%)	234 (18.7%)	0.1379
Secondary Outcomes			.
AKI Progression	162 (13%)	194 (15.5%)	0.0762
Dialysis	29 (2.3%)	35 (2.8%)	0.4714
Death	73 (5.9%)	67 (5.4%)	0.6142
Discharge to Home	688 (55.3%)	660 (52.8%)	0.1791
Length of Stay, days after randomization	3.4 (1.6,7.7)	4 (1.9,8.2)	0.3585
Duration of AKI, days			0.8928
<2 days	926 (74.4%)	930 (74.4%)	.
2 - <7 days	275 (22.1%)	272 (21.8%)	.
7+ days	43 (3.5%)	48 (3.8%)	.
Max AKI Stage Achieved			0.8527
Stage 0	2 (0.2%)	2 (0.2%)	.
Stage 1	985 (79.2%)	982 (78.6%)	.
Stage 2	155 (12.5%)	165 (13.2%)	.
Stage 3	102 (8.2%)	101 (8.1%)	.

Outcome Table
YNH

Variables	Control (N=462)	Alert (N=449)	p-value
Primary Outcome			

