A group sequential design with Hwang-Shih-DeCanli spending functions with gamma = -4 for the efficacy boundary and gamma = -2 for the futility boundary with two interim analyses will be utilized and a two-sided Cochran-Mantel-Haenszel (CMH) method will be used for the sample size calculation to account for the four hospitals. Our preliminary data suggests that 18.2% of patients would experience the primary outcome of progression of AKI, dialysis, or mortality. We determined that a relative 20% reduction to 14.6% would be clinically significant. A total sample size of 4600 patients (i.e., 2301 per group) achieves at least 90% power to detect this degree of change. The alpha significance level of the test was set at 0.05. We will increase this

number by 10% to account for potential contamination of the effect across study arms, leading to a final sample size of 5060 individuals with a breakdown as follows based on relative numbers of beds in each hospital:

Yale New Haven Hospital: 2447

St. Raphael's Campus: 1214

Bridgeport Hospital: 910

Greenwich Hospital: 489

We will compare the rates of the primary outcomes between the intervention arm and the control arm using the chi-square test with Cochran-Mantel-Haenszel correction for the 4 study strata based on the hospital.. We will also perform exploratory analyses examining patients within the three medication categories to assess whether discontinuation rates differ by medication and, importantly, what clinical impact is apparent from alerting for those particular agents. Finally, should alerting show a clinical benefit, we will perform a mediation analysis to determine what fraction of that benefit (if any) can be attributed to medication cessation.

In addition, a retrospective examination will be performed to assess improvement in the control group before / after intervention as a measurement of contamination. We expect that providers who receive AKI alerts on some patients may be more likely to look for AKI in other patients, potentially diluting the effect of the intervention – this pre/post intervention analysis will help in assessing that level of contamination.

Because we are enrolling patients across four sites, we will do an exploratory analysis to determine the efficacy of alerts independently at each hospital.

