We have specified several subgroups in whom the benefit of an AKI alert may differ from the general population. These groups will be analyzed as secondary and exploratory analyses. They include:

- Patients with AKI exposed to each of the 3 nephrotoxin categories (effects analyzed separately)
- Surgical patients (defined by admission to a surgical team)
- Subjects with baseline creatinine <1.0mg/dl
- Subjects with baseline creatinine <0.5 mg/dl
- Females (due to lower rate of increase in creatinine after AKI)
- African Americans (due to higher rate of increase in creatinine after AKI)
- Elderly subjects (age > 65, age > 70, and age > 75)
- Subjects in an ICU at the time of the alert
- Subjects who enter the study based on a 50% increase in creatinine vs. a 0.3mg/dl increase in creatinine vs. both

Finally, as the academic year progresses, new clinicians (such as residents and interns) may become more facile in their ability to recognize AKI, which may attenuate the effect of this intervention. We will model this in exploratory analyses using an intervention-by-time of year interaction term in models of the primary outcome.

Interim Analysis:

As discussed above, we plan an interim analysis, and guidelines will be given to the DSMB for stopping the trial will be for efficacy, harm, and futility. Our interim analyses will be conducted as follows:

This interim analysis will be performed at 50% enrollment at the four teaching hospitals and the trial will stop for either efficacy or futility if the p-value is $\leq .0042$ or $\geq .8952$. The p-value threshold for the final analysis of the primary outcome is set at .0498.

SECTION II: RESEARCH INVOLVING DRUGS, BIOLOGICS, RADIOTRACERS, PLACEBOS AND DEVICES

If this section (or one of its parts, A or B) is not applicable, check off N/A and delete the rest of the section.

A. RADIOTRACERS N/A

B. DRUGS/BIOLOGICS N/A

B. DEVICES N/A

SECTION III: RECRUITMENT/CONSENT AND ASSENT PROCEDURES

1. Targeted Enrollment: Give the number of subjects:

- Targeted for enrollment at Yale for this protocol: 1915 patients and approximately 2500 clinicians
- If this is a multi-site study, give the total number of subjects targeted across all sites: 4592 patients and approximately 3500 clinicians

2. Indicate recruitment methods below. Attach copies of any recruitment materials that will be used.

 Flyers	 Internet/web postings	 Radio

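### The before/after change in control patients is labelled a measurement of contamination, but without a concurrent comparison it mixes contamination with other changes the protocol itself names

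*Combined protocol and SAP*

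**What the plan says.** All references are to the combined protocol and SAP. After the primary analysis, Section I, 13 (Statistical Considerations) adds that "a retrospective examination will be performed to assess improvement in the control group before / after intervention as a measurement of contamination". The mechanism it has in mind is that clinicians alerted on some patients look harder for AKI in others, and it concludes that "this pre/post intervention analysis will help in assessing that level of contamination". It does not state a window before activation, an outcome, a model, an adjustment for trend or case mix, or a comparison group.

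Other sections bear on how such a change can be read:

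- Section I, 13 notes that as the academic year goes on new clinicians "may become more facile in their ability to recognize AKI, which may attenuate the effect of this intervention". An exploratory interaction term is planned for this in models of the primary outcome. It is not tied to the before/after check.
- Section I, 4 (Clinician Outreach) plans education before and during the trial for all clinicians who may be exposed.
- Section I, 10 (Risks) recognises that, as providers learn that alerts exist, it is possible that "they become less attentive to the presence of AKI in patients randomized to the usual care group".
- Section I, 3 (Background) reports a randomised trial of "electronic alerts for AKI throughout the Yale New Haven Health System from 2018 to 2020". For safety, Section I, 11 says "we analyzed a subset of data from our initial alert trial, including only patients who meet criteria for the current study", and its tables include the four hospitals of the present trial.
- Section I, 4 (Study Timeline) says "We plan to activate our medication-targeted alert in a step-wise fashion throughout our 4 study hospitals". The reasons given are education, monitoring and quality control, not analysis.

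**The concern.** Randomisation begins when the alert build goes live, so no control group exists before activation. The earlier group must be other patients treated at another time, and any difference between the two groups reflects everything that changed in between. The plan gives that whole difference one name.

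What is at stake is what the trial may say about dilution. If control care improves through learning or outreach, the check would report contamination that did not come from the alerts, and a small treatment effect could be put down to dilution. If inattention offsets real contamination, a flat result would suggest there was none. In both cases the figure is mislabelled when the plan is followed as written.

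**Working it through.** **1. The plan's figures.** The before/after check has no stated figure to reproduce. The related ones agree: the planned effect is 18.2 − 14.6 = 3.6 points, 4600 × 1.10 = 5060, and the hospital targets 2447 + 1214 + 910 + 489 sum to 5060. Half of that is 2530 expected controls.

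**2. What the change contains.**

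| Source of change | Section | Likely effect on control care | Removed by a before/after comparison? |
|---|---|---|---|
| Alerted clinicians look for AKI in other patients | I, 13 | improves | this is the target |
| Academic-year learning | I, 13 | may improve | only if calendar months are matched |
| Outreach before and during the trial | I, 4 | may improve | no, if it starts after the window |
| Inattention to usual-care patients | I, 10 | may worsen | no, it starts with activation |
| Earlier alert trial, 2018 to 2020 | I, 3 | depends on the window | only if the window avoids it |

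There is one observed difference and several unknowns, with differing signs. No single value identifies the first row.

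**3. Illustration of the ambiguity.** The plan names no outcome, so the primary outcome is assumed here. Suppose the control rate falls by d from 18.2%, with n = 2530 per arm. Then

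power = Φ{[|p₁ − p₂|√n − 1.96√(2p̄q̄)] / √(p₁q₁ + p₂q₂)},

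ignoring strata and the interim look. With d = 0 it is 93.3%. If the fall is contamination, the alert arm stays at 14.6%. If it is background change, the 20% relative effect is kept.

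| d (points) | d / 3.6 | Power if contamination | Power if background |
|---|---|---|---|
| 0.5 | 14% | 85.0% | 93.1% |
| 1.0 | 28% | 71.5% | 92.3% |
| 1.5 | 42% | 53.8% | 91.4% |

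The check returns the same d in both columns.

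**4. Dependence on the baseline.** From the Section I, 11 tables for the four hospitals:

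- controls: (92 + 39 + 38 + 17)/(462 + 282 + 188 + 142) = 186/1074 = 17.3%
- alerted: 208/1086 = 19.2%
- both arms: 394/2160 = 18.2%
- reweighted to the plan's hospital shares (48.4/24.0/18.0/9.7%): controls 17.7%, both arms 18.7%

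Take a new control rate of 17.3%, chosen to equal the first baseline. Against controls, reweighted controls, both arms and reweighted both arms, the falls are 0, 0.42, 0.92 and 1.36 points. Divided by 3.6, these read as 0%, 12%, 26% and 38% of the effect lost. The earlier arms differ within chance (1.83/1.66, z = 1.10), so the spread shows sensitivity to the choice, not a real shift.

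**5. Precision of the uncontrolled check.** 95% half-widths against 2530 new controls:

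- 1074 earlier controls: 1.96√[0.1732 × 0.8268 × (1/1074 + 1/2530)] = 2.7 points (75% of 3.6)
- 2160 earlier patients: 1.96√[0.1824 × 0.8176 × (1/2160 + 1/2530)] = 2.2 points (62%)
- earlier rate known exactly: 1.96√(0.182 × 0.818/2530) = 1.5 points (42%)

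**6. Precision of a controlled version.** Weighted least squares on hospital-by-month cells, with hospital, month and activation terms. Assumed: 12 months before and 24 after first activation, 5060/24 = 211 eligible patients a month, all eligible patients used before activation, half of them (the controls) afterwards, and the largest hospital first. At 18.2% the half-width is 8.5, 6.2, 5.2 or 4.1 points for steps of 1, 2, 3 or 6 months; with the smallest hospital first it is 9.3 down to 4.3. For cessation within 24 hours, Section I, 3 gives continuation of 92%, 66% and 59% by drug class, hence cessation of 8% to 41%. The half-width is then 2.9 to 10.8 points (largest hospital first).

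**The case against.** The check is supplementary. No adjustment, decision or stopping rule uses it, and its second sentence claims only that it will help. That stands as a limit on importance, but the first sentence still calls the change a measurement.

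Three stronger readings are tempting and are not supported:

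- *Every possible baseline is contaminated.* The earlier trial's months and the activation dates are not given, so an alert-free interval between them is not ruled out. In the earlier subset at these hospitals 1086 of 2160 patients were alerted, but Section I, 3 describes that alert as informational and reports no difference in process measures between arms. Spill-over could itself produce such equality, so this neither shows nor excludes contamination.
- *The plan predicts a steady improvement in recognition.* It says only that this may happen, over the academic year. Matching calendar months would remove the seasonal part.
- *The check could rescue a null trial.* Section I, 10 says "Should no effect be found in these studies, AKI alerts will not be continued at the institutions", with no exception for contamination. Explaining a null result by dilution is a risk of interpretation, not a provision of the plan.

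It is also fair that outreach could be counted as spill-over of the trial. It is still not the alert-exposure mechanism that Section I, 13 describes.

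Finally, the controlled comparison is no cure. Inattention and contamination both begin at activation, so it estimates their net effect. Outreach may reach hospitals still waiting. On the primary outcome it is less precise than the uncontrolled check. All of this stands, and it is why the label matters more than the model.

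**Conclusion.** The point holds as one of labelling and identification. An uncontrolled before/after change in controls is a net figure and should not be called a measurement of contamination when the same document names other sources of change. This is more than missing detail, because following the text yields a mislabelled result. The randomised comparison of arms is untouched.

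The sizes are illustrations. They rest on the primary outcome as an assumed measure, on assumed falls of 0.5 to 1.5 points (14% to 42% of the planned effect) and on assumed baselines. The contamination mechanism concerns process, so a process measure is the better outcome. The change is worth making before the data are examined, at moderate priority.

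**What to change.** Replace the two sentences in Section I, 13 with text to this effect:

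> Change over time in control-group care will be described by hospital and calendar month. The before group is patients who meet the same electronic criteria in a dated window before activation at each hospital; any overlap with the earlier alert trial will be flagged. The main outcome is medication cessation within 24 hours; the primary outcome is descriptive only. As a supporting analysis, a model with hospital, calendar-month and activation terms will use hospitals not yet activated as the concurrent comparison. Results will be given with 95% intervals. An uncontrolled before/after change will not be reported as contamination, or used to adjust or explain the treatment effect.

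State the limits beside it: the model estimates the net of contamination and inattention; outreach before the trial may reach waiting hospitals; and on the primary outcome a half-width of about 4 to 8 points, under the assumptions above, is too wide to size dilution of a 3.6-point effect.

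The cost is a dated extract from the same records and one added model, with no extra patients and no change to the primary analysis. The plan gives up a single simple contamination figure, and the controlled estimate is imprecise. If the model is not wanted, the relabelling alone corrects the main error.

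### Section I.13 derives a total of 5060 patients, but Section III.1 states 4592 in all and 1915 at an undefined Yale, and nothing reconciles them

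*Combined protocol and SAP*

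**What the plan says.** Section I, item 13 starts from 4600 patients, stated to give at least 90% power for 18.2% against 14.6% at an alpha of 0.05. It then enlarges that base, raising the "number by 10% to account for potential contamination of the effect across study arms". The step is described as "leading to a final sample size of 5060 individuals with a breakdown as follows", and the hospital targets are listed after it: "Yale New Haven Hospital: 2447", with 1214 at St. Raphael's, 910 at Bridgeport and 489 at Greenwich.

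Section III, item 1 gives two other patient numbers. The first line reads "Targeted for enrollment at Yale for this protocol: 1915 patients and approximately 2500 clinicians". The second, for a multi-site study, asks the applicant to "give the total number of subjects targeted across all sites: 4592 patients and approximately 3500 clinicians". Neither figure is derived, and Yale is not defined in that item.

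Under Interim Analysis in Section I.13, the timing of the look is a fraction and not a count: "This interim analysis will be performed at 50% enrollment at the four teaching hospitals". Items 11 and 12 of Section I also give it as a percentage.

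No text links the two sets of numbers or says that one supersedes the other.

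**The concern.** A trial should have one target sample size, and here the current text has two. They differ by almost exactly the allowance that Section I.13 adds on purpose, because it expects alerted clinicians to look harder for AKI in control patients as well. If 4592 were the operative number, that allowance would be missing while Section I.13 still said it was included. The stated half-way point would also move, because 50% of enrollment is a different number of patients under each total. The Yale figure is a second mismatch, and it would remain even if the difference in totals were explained by the missing 10%.

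**Working it through.** **Inputs.** From Section I.13: control rate 0.182, alert rate 0.146, two-sided alpha 0.05, base total 4600, inflation 10%, site targets 2447, 1214, 910 and 489, interim thresholds p ≤ .0042 and p ≥ .8952, final threshold .0498, one look at 50%. From Section III.1: total 4592, Yale 1915.

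**1. The plan's own total.**
- 4600 × 1.10 = 5060.
- 2447 + 1214 + 910 + 489 = 5060.

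Section I.13 is consistent with itself.

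**2. The base of 4600.** The fixed-design size per group, with pooled variance under the null and mean rate 0.164, is

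n = [1.960·√(2·0.164·0.836) + 1.282·√(0.182·0.818 + 0.146·0.854)]² / 0.036² ≈ 2222,

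or 4444 in total. A group sequential design needs somewhat more, so 4600 is a plausible base.

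**3. Section III.1 against Section I.13.**
- 5060 − 4592 = 468, and 468/5060 = 9.2%.
- 4600 − 4592 = 8.
- Could 4592 already contain the 10%? 4592/1.10 ≈ 4175, which is below the 4444 needed even with no interim look. On Section I.13's assumptions it could not.

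**4. The Yale figure.**
- Yale New Haven Hospital alone: 2447.
- With St. Raphael's: 2447 + 1214 = 3661.
- The same two with the 10% removed: 2447/1.10 ≈ 2225 and 3661/1.10 ≈ 3328.

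None is 1915, and no other sum of the site targets gives it.

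**5. Interim timing.** Half of 5060 is 2530 and half of 4592 is 2296, a difference of 234 patients.

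**6. Power without contamination, under the thresholds stated in Section I.13.** Normal approximation, equal arms, hospital strata not modelled, one look at exactly 50%. The critical values are 2.863 at the look (p = .0042) and 1.962 at the end (p = .0498). The p = .8952 futility line corresponds to |z| = 0.132.

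| Handling of the p ≥ .8952 rule | 4592 | 5060 |
|---|---|---|
| Not enforced | 91.0% | 93.3% |
| Enforced on the two-sided p-value | 90.7% | 93.1% |
| Enforced, negative trends also stop | 90.6% | 93.0% |

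Both totals meet the stated 90% before any contamination. The difference between them is a little over two percentage points.

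**The case against.** The strongest reply is that this is a form field that was not updated. Section I.13 calls 5060 the final sample size, derives it and splits it by hospital. The interim is specified in the same item, so 50% most naturally means 2530. No analysis or stopping rule mentions 4592. This stands as an account of how the mismatch probably arose and of which number to believe. It does not remove the conflict, because the document never says so, and a missing 10% would not explain 1915.

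Three stronger readings are tempting, and the documents do not support them.

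- **That 4592 leaves the trial below 90% power.** This requires following a gamma = -2 futility boundary at the look. Section I.13 names that spending function, but on recalculation its bound at 50% falls at a two-sided p of about .68 to .69, whereas the stated stopping value is .8952. Even then the shortfall does not come from Section III.1. With one look and that boundary followed, power is about 89.8% at 4592 and also at 4600. With two equally spaced looks it is about 89.2% at both. Any such question concerns the 4600 base.
- **That contamination would cost a known amount of power at 4592.** The protocol states no level of dilution, so any such figure would rest on a level chosen by the reader.
- **That the discrepancy undermines the request to waive patient consent.** The waiver answers rest on minimal risk, rights and welfare, and impracticability. None depends on whether the total is 4592 or 5060.

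It could also be argued that the interim trigger should be restated as a patient count. That is unnecessary once there is one total.

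**Conclusion.** The inconsistency is real and should be corrected. Two numbers in Section III.1, the total and the Yale figure, conflict with Section I.13. The total is low by 468 patients (9.2%). The Yale figure is low by 532 (2447 − 1915) if it means Yale New Haven Hospital alone, or by 1746 (3661 − 1915) if it includes St. Raphael's.

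The arithmetic of Section I.13 is sound, and 5060 is the natural reading. That Section III.1 is the item in error is an inference: it is likely, but not stated. If 4592 were in fact the target, power without contamination would still be about 91%, against 93% at 5060. The loss would be the margin that the plan says it has built in against contamination. These power figures assume the stated event rates, equal arms, one look at 50% and the stated p-value thresholds.

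The mismatch between two interim analyses in the design statement and the single look described under Interim Analysis is a separate matter, and this point does not depend on it.

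**What to change.** Correct the all-sites total in Section III, item 1 to 5060. Define Yale in that item and give the Section I.13 figure that matches the definition: 2447 for Yale New Haven Hospital alone, or 3661 with St. Raphael's. The references to 50% enrollment in items 11, 12 and 13 of Section I then all point to one total and need no change.

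If 4592 is the intended total, make the correction in Section I.13 instead: change the final total and the four site targets, and remove the statement that the size allows for contamination. The Yale entry would still need a definition and a figure that agrees with the revised site targets.

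The cost of the first option is a wording change and a corrected enrollment figure for the IRB. It adds no patients to the 5060 already planned in Section I.13, although 5060 is 468 more than the present Section III.1 entry (468/4592 = 10.2%).
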